### **7.2.5 Responsibility for Reporting Adverse Events**

All Adverse Events will be reported to regulatory authorities, IRB/IECs and investigators in accordance with all applicable global laws and regulations.

## **8.0 DATA AND SAFETY MONITORING PLAN**

### **8.1 JCCC DSMB Oversight**

This trial will be overseen by the JCCC DSMB. The JCCC DSMB meets monthly to review all SAE reports for trials overseen by the JCCC DSMB. All SAE reports, which have been filed since the previous meeting, are presented to the committee for review.

For trials overseen by the JCCC DSMB, the DSMB reviews all dose-limiting toxicities (DLTs) for dose-escalation studies. Protocol suspensions and re-opening of accrual to the next cohort based on DLT evaluation fall under the purview of the DSMB.

For all JCCC oncology trials and TRIO-US studies where the JCCC DSMB has primary oversight, all SAEs shall be reported to the JCCC DSMB in a timely manner [ten days, two days for a death] regardless of relationship and expectedness. The JCCC ORC will review all submissions and the ORC staff will enter the information into the JCCC Clinical Trials database. Reports are generated for full JCCC DSMB review. For trials where the JCCC DSMB has primary DSMB review responsibility, the DSMB requires that the PI generate cumulative adverse event reports for quarterly, biannual or annual review.

The DSMB reviews each SAE report and determines whether or not protocol modifications are warranted to ensure subject safety. In this review, prior occurrences of similar toxicity with the therapy under study are taken into consideration, as well as the severity of the event and the likelihood that it was related to a study drug. The DSMB may recommend no changes to the study if the event is expected or related to other causes such as the subject's underlying condition. The DSMB may request an expert's advice of another non-Principal Investigator with national experience to support their deliberations and decisions.

The JCCC DSMB has the authority to recommend to the UCLA IRB the immediate halt to a study (i.e., discontinuation of any further treatment of enrolled subjects and discontinuation of enrollment of new subjects) should there be any serious unexpected toxicity that warrants further investigation.

Requests for single subject exceptions/waivers from the approved study protocol, including out of window procedures and eligibility deviations, must be reviewed and approved by a member of the DSMB. Each trial is assigned a primary and secondary reviewer who is responsible for reviewing each exception/waiver request for that trial. Approvals and disapprovals of the request are sent to the Principal Investigator via email and copied to the UCLA IRB. Requests for single subject exceptions/waivers are made by the Principal Investigator via email utilizing the "Single Subject Exception Request Form."

JCCC DSMB correspondences are addressed to the Principal Investigator and copied to the UCLA IRB. Minutes of the DSMB meetings are maintained in a computer file.

**Confidentiality:** Each member of the JCCC DSMB is responsible for maintaining strict confidentiality of the study data. Members will not share any study data or information about the study with any individual external to the JCCC DSMB or the statistical working group for the study. The DSMB members may contact the statistical working group directly with questions regarding the operational details associated with the data analysis and summary presentations. Communication of deliberations or recommendations of the JCCC DSMB, either written or oral, should not be made outside of the Committee or the statistical working group. Outcome results are strictly confidential and must not be divulged to any non-member of the JCCC DSMB except in those cases where DSMB is required to inform the UCLA IRB of its determinations. Disclosure of outcome results to the IRB must only occur with written approval of the DSMB. A member who believes he or she may have a potential intellectual or financial conflict of interest during the course of review of the data must inform the chairperson of the DSMB. In such case, the meeting minutes will record the disclosure of the potential conflict of interest and that the individual recuse himself from the discussions and abstains from voting on the DSMB decision.

## **8.2 Assignment of Risk – Level 2**

All interventional clinical trials undergo scientific review by the Internal Scientific Peer Review Committee (ISPRC) which requires that a Data and Safety Monitoring Plan is in place before a trial can be approved to begin. For trials overseen by the JCCC DSMB, the JCCC DSMB will determine the degree of risk of the study and will ensure that there are procedures in place to ensure the safety of the subjects that are enrolled in the trial. The intensity level of study oversight is determined by the risk category. Some of the factors that are considered when assigning the Level of Risk category include:

- A biostatistical design and appropriate procedures for proper data management so that the information collected can be properly validated.
- Appropriate Serious Adverse Event reporting procedures must be in place.
- The study duration must be appropriate and must be based on a realistic rate of enrollment.
- Data collection and data management must be adequate to verify and ensure subject eligibility.

### **8.2.1 Assignment of Risk**

This protocol is assigned a Level 2 Risk. Assigning risk ensures that the data and safety monitoring is based on the level of risk (low, medium, or high) to ensure that the data and

safety monitoring activities are appropriate. Level 2 Risk assignment includes the data and safety monitoring activities listed below:

- Compliance Officer meets with PI/Staff prior to study initiation; review regulatory requirements and operating system. Compliance Officer provides real time monitoring to determine eligibility prior to enrollment onto the protocol.
- Real time QA monitoring of the subjects and data collection occurs for all subjects entered onto the trial.
- Comprehensive QA auditing within first year or first 10 subjects enrolled, whichever comes first. Subsequent audit frequency will be annually.
- Frequency of DSMB Summary Report is typically on a biannual basis or approximately every six months.

### **8.3 Monitoring and Auditing Activities**

The compliance officer of the JCCC Office of Regulatory Compliance [ORC] will monitor and audit the clinical records for all human subjects enrolled onto JCCC trials overseen by the JCCC DSMB. The JCCC compliance officer will perform real time review of informed consent processes and the meeting of all inclusion and exclusion criteria and screening results at study entry. Active monitoring will offer the JCCC study teams prospective information that can be used to enhance the quality of research being performed contemporaneously. Auditing is a review of historic performance of the research effort and is performed on case report forms, regulatory files and source documents to measure the quality of the research effort in a retrospective manner.

## **9.0 STATISTICAL ANALYSIS PLAN**

### **9.1 Efficacy Endpoints**

#### *Primary*

The primary efficacy analyses will be based on the Full Analysis Set (FAS). Patients with measurable disease at baseline who received at least one dose of study treatment will be included in the FAS. The primary efficacy endpoint is objective response rate (ORR) and will be determined by blinded central review. We will use an exact binomial test to evaluate the response rate to the null hypothesis value of 0.10.

Response duration is defined as the time from first documented evidence of response until progression, according to RECIST 1.1. Objective response rate is determined as the proportion of patients achieving complete response (CR) or partial response (PR) as respectively defined in RECIST 1.1. A 95% confidence interval will be provided for the objective response rate of the population. All patients

receiving at least one dose of pembrolizumab will be considered evaluable for efficacy and toxicity.

### *Secondary*

Secondary efficacy endpoints, progression free survival and overall survival, will also be analyzed. Per RECIST 1.1, progression free survival (PFS) is defined as time from randomization to first documented progression and overall survival (OS) and is defined as time from randomization to death by any cause.

For patients harboring EGFR-sensitizing mutations, PFS, ORR, OS following TKI therapy will be assessed and analyzed against data on treatment-naïve EGFRm NSCLC treated with TKI as control.

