**EudraCT NUMBER (Studies in Europe only):**

**NCT Number: NCT02879994**

**Version 4      01 December 2017**

## 1.0 TRIAL SUMMARY

Abbreviated Title	Pembrolizumab in Frontline EGFR mutant, TKI-naïve NSCLC
Trial Phase	Phase II
Clinical Indication	The treatment of subjects with non-small cell lung cancer (NSCLC) whose tumors are positive for PD-L1 and harbor an EGFR mutation who have not been previously treated with an EGFR TKI
Trial Type	Interventional
Type of control	Active control without placebo
Route of administration	Intravenous
Trial Blinding	Unblinded Open-label
Treatment Groups	Pembrolizumab 200 mg every three weeks
Number of trial subjects	Approximately 25 patients will be enrolled.
Estimated enrollment period	We estimate that the trial will require approximately 16 months from the time the first subject signs the informed consent until the last subject's consent.
Estimated duration of trial	We estimate that the trial will require approximately 28 months from the time the first subject signs the informed consent until the subject's last visit.
Duration of Participation	Each subject will participate in the trial from the time the subject signs the Informed Consent Form (ICF) through the final protocol-specified contact. After a screening phase of up to 28 days, eligible subjects will receive assigned treatment on Day 1 of the 3-week (Q3W) dosing cycle. Treatment with pembrolizumab will continue until radiographic progression, documented disease progression, unacceptable adverse event(s), intercurrent illness that prevents further administration of treatment, investigator's decision to withdraw the subject, subject withdraws consent, pregnancy of the subject, noncompliance with trial treatment or procedure requirements, or administrative reasons. After progression on pembrolizumab, patients will be asked to undergo an additional biopsy and blood draw and be followed through periodic follow-up visits and calls (every 60 days) for evaluation of duration of response with the EGFR TKI as well as survival follow up
Estimated average length of treatment per patient	6 months

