#### 3.2 Secondary Objective(s) & Hypothesis(es)

- (1) **Objective:** Determine safety [adverse event tabulation and grading] of front-line pembrolizumab for Stage IIIB or IV EGFR mutation positive PD-L1+ [ $> 1\%$  by immunohistochemistry (IHC)]NSCLC
- (2) **Objective:** Determine efficacy [progression free survival (PFS), overall survival (OS)] of front-line pembrolizumab for Stage IIIB or IV EGFR mutation positive PD-L1+ ( $>1\%$  by IHC) NSCLC
- (3) **Objective:** Determine ORR, PFS and OS of subsequent EGFR TKI therapy in patients with EGFR-sensitizing mutation after pembrolizumab

**Hypothesis:** We hypothesize that the safety, progression free survival, and overall survival among EGFR mutant patients who are EGFR TKI naïve and treated with pembrolizumab will be similar to what has been generally seen with pembrolizumab in the general population. Further, we hypothesize that the clinical outcomes from EGFR TKI treatment in patients with EGFR-sensitizing mutations after pembrolizumab will be similar to what would be expected in a treatment naïve patient population.

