#### *Epidermal Growth Factor Receptor: Mutations and Targeted Therapies*

Tyrosine kinase receptors play a major role in the tumorigenicity of neoplastic cells, particularly NSCLC (4). Up to half of NSCLC patients in Asian populations and approximately 10% in Western populations harbor EGFR mutations (5-6). To stop the proliferative signals of EGFR, TKIs such as gefitinib, erlotinib, and afatinib selectively block autophosphorylation of the EGFR intracellular tyrosine kinase domain (7). These drugs are approved in multiple countries for the treatment of locally advanced or metastatic NSCLC in 2nd or 3rd-line therapy.

Gefitinib showed superiority as a first line therapy compared to carboplatin-paclitaxel chemotherapy in progression-free survival (PFS) in EGFR mutant patients (hazard ratio (HR) for progression, 0.48;  $p < 0.001$ ) (8). As a result, EGFR TKIs have become the standard initial therapy in EGFR mutant NSCLC. Although there have been meta-analyses and subset analyses that have found improvement in survival with an EGFR TKI, individual studies have failed to show improvement in overall survival for EGFR TKIs in EGFR mutant patients, presumably based on patients in the chemotherapy arms crossing over to EGFR TKIs on progression (9).

Second generation TKIs including dacomitinib and afatinib have been evaluated (10-11). However, in approximately 60% of EGFR mutant patients, resistance is mediated by a secondary T790M mutation in EGFR, and 2nd generation agents have not been clinically successful in this setting (12).

Third generation drugs, including CO-1686 and AZD9291, have been designed to irreversibly inhibit the tyrosine kinase activity of mutant EGFR without affecting wild-type EGFR (13-15). Phase I/II trials are currently underway (NCT01526928 and NCT01802632), with preliminary data indicating over 50% objective response rate (ORR) in T790M-positive patients (16-17). However, this accounts for only a subset of patients with TKI resistance, leaving a significant proportion of patients without favorable options after progression on an EGFR TKI. Moreover, acquired resistance to these new agents is anticipated.

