In order to corroborate the results from the clinical trial, we conducted cell line experiments to evaluate potential immunomodulatory effects of EGFR TKIs, particularly with respect to the PD-1 pathway (Figure 1). Afatinib, an irreversible pan-HER inhibitor is associated with an  $IC_{50} < 1\mu M$  in H1975, HCC827 and Calu-3. Erlotinib, a reversible EGFR inhibitor, inhibits only HCC827 at this level. Neither TKI inhibits H460 at this level. The cell lines that were effectively inhibited by the EGFR TKI also saw a decrease in PD-L1 levels, confirming results from others (23). When studying TKI-resistant, non-small cell lung cancer cell lines, PD-L1 expression was not reduced by EGFR TKIs. The results mimic what we saw clinically, in which pembrolizumab was not an effective therapy in patients with EGFR sensitizing mutations after a prior EGFR TKI.

[figure not shown]

Figure 1: Western blot analysis of PD-L1 expression (PD-L1 mAb #13684, Cell Signaling Technology) in NSCLC cell lines in response to erlotinib and afatinib. NSCLC cell lines H1975 (EGFR L858R/T790M mutation), H460 (KRAS Q61H mutation), HCC827 (EGFR exon 19 deletion), and Calu-3 (*her2* amplification) were evaluated at

baseline and after 24 hours of exposure to 1  $\mu$ M erlotinib or afatinib. \* indicates an  $IC_{50} < 1 \mu$ M for the respective drug in that cell line.

Data from the KEYNOTE 024 trial showed that first-line treatment with pembrolizumab significantly improved progression-free and overall survival in patients with PD-L1 positive (>50%) non-small cell lung cancer. Pembrolizumab was also associated with a higher overall response rate and a longer duration of response than platinum-based chemotherapy. Patients with EGFR mutations were excluded from this study (37).

This study will be the first to our knowledge to evaluate the role of PD-1 inhibitors in EGFR mutant patients who have not yet received an EGFR TKI. After progression on pembrolizumab, patients will be asked to undergo an additional biopsy and blood draw and be followed through periodic follow-up visits and calls (~every 2 months) for evaluation of duration of response with the EGFR TKI as well as survival follow up. The goal of this clinical trial is to evaluate a treatment sequence in which EGFR mutant NSCLC patients receive pembrolizumab prior to an EGFR TKI.

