### **4.2.3 Rationale for Endpoints**

#### **4.2.3.1 Efficacy Endpoints**

The primary endpoint will be objective response rate (ORR), while the secondary endpoints will be progression-free survival (PFS) and overall survival (OS). The rationale for using ORR as the primary endpoint is that this trial is a single-arm trial; assessing ORR will allow us to attribute the effect of treatment directly to pembrolizumab, not to the natural history of NSCLC.

Since ORR cannot comprehensively measure drug activity, PFS and OS will be used as secondary endpoints. This will allow us to account for deaths that are unrelated to cancer and to the effects of pembrolizumab. PFS is an acceptable measure of clinical benefit for a Phase 2 trial that demonstrates superiority of a new antineoplastic therapy, especially if the magnitude of effect is large and the therapy has an acceptable risk-benefit profile. Furthermore, it is an endorsed regulatory endpoint for 1L NSCLC trials with recent FDA and EMA approvals including the EGFR inhibitors afatinib and erlotinib. PFS will be assessed by RECIST 1.1 by an independent central radiologists' review. Although PFS assesses how long a patient is on trial without progressing, since we have seen that EGFR mutant patients have

a high response rate, we will also collect OS data to determine if pembrolizumab is comparable to TKI therapy or standard of care chemotherapy. Further, OS is a standard assessment of clinical benefit in subjects with advanced or metastatic NSCLC. OS will be assessed by RECIST 1.1 criteria by independent central radiology review.

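### The post-TKI comparison in Section 9.1 is conditional on starting a TKI, so it cannot evaluate the pembrolizumab-first sequence

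*Combined protocol and SAP*

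**What the plan says.** - **Goal.** Section 4.2.1: "The goal of this clinical trial is to evaluate a treatment sequence in which EGFR mutant NSCLC patients receive pembrolizumab prior to an EGFR TKI".
- **Objective and hypothesis.** The third secondary objective in Section 3.2 is: "Determine ORR, PFS and OS of subsequent EGFR TKI therapy in patients with EGFR-sensitizing mutation after pembrolizumab". The matching hypothesis is that these outcomes "will be similar to what would be expected in a treatment naïve patient population". No margin is given.
- **Analysis.** Section 9.1 says, for patients with sensitizing mutations, that PFS, ORR and "OS following TKI therapy will be assessed and analyzed against data on treatment-naïve EGFRm NSCLC treated with TKI as control". It does not define the analysis set, the time origin after TKI start, the handling of patients who never start a TKI, or the control source.
- **OS.** Section 9.1 gives one definition: OS "is defined as time from randomization to death by any cause". Section 7.1.1.7 states that the trial is not randomized. Section 4.2.3.1 gives the purpose: "we will also collect OS data to determine if pembrolizumab is comparable to TKI therapy or standard of care chemotherapy". Section 9 contains no such comparison.
- **Timing.** Section 1.0: "We estimate that the trial will require approximately 28 months from the time the first subject signs the informed consent until the subject's last visit". It also gives about 16 months of enrolment and an average of 6 months on treatment. Section 5.6 allows treatment for 24 months or 35 administrations, whichever is later.

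**The concern.** Starting a TKI is a post-baseline event. A sensitizing-mutation patient who dies or declines on pembrolizumab before a TKI contributes nothing to the post-TKI analysis. Nor does a patient still on pembrolizumab when the study ends. The control patients have passed through no such filter.

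A finding that TKI results resemble those in untreated patients could therefore be reported even if giving pembrolizumab first had cost some patients their chance of a TKI. That loss is a central risk of the sequence, and this analysis cannot see it. All-patient OS could show it, but Section 9 does not set it against TKI-first data. Section 4.2.3.1 also interprets it as a property of pembrolizumab alone, although sensitizing-mutation patients may go on to a TKI.

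**Working it through.** **1. The plan's own figure.** Section 9.6 covers only the primary ORR test: n = 25, 10% against 26%, one-sided 0.10, power 81%. The exact binomial rule of at least 5 responses in 25 gives alpha 0.098 and power 0.817, so the figure reproduces. The TKI comparison has no stated size, margin or power. What follows is illustration under stated assumptions.

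**2. Who can enter.** Section 4.2.1 puts the share of EGFR-mutant patients without a TKI-sensitive mutation at about 10%. So 25 × 0.90 = 22.5, taken as 22. Section 5.1.2 admits both mutation types, so the real number may differ. The last patient enrolled has about 28 − 16 = 12 months of observation, so some patients may still be on pembrolizumab at study end. With a 6-month average on treatment, how many is unknown.

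**3. Denominator.** Let d be the deaths before a TKI (assumed), with every other patient starting one, and let post-TKI survival at 12 months be 70% (assumed). The share of the 22 alive at TKI start plus 12 months is 0.70 × (22 − d)/22.

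| d | (22 − d)/22 | Share of all 22 |
|---|---|---|
| 2 | 0.91 | 64% |
| 4 | 0.82 | 57% |
| 6 | 0.73 | 51% |

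If the TKI starts at about month 6, these are figures for about month 18 of the sequence. They are not directly comparable with 12-month survival on TKI-first care.

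**4. Survivor conditioning alone.** Assume that the sequence has no effect on survival and that only death prevents a TKI. Take S(t) = (1 + θλt)^(−1/θ), exponential when θ = 0, with true median m and TKI start at t0. The median u after TKI start solves S(t0 + u)/S(t0) = 0.5.

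- For m = 24, t0 = 6, θ = 0: the share reaching a TKI is 2^(−6/24) = 0.841. The median is 24.0 months from TKI start, or 30.0 from enrolment.
- For m = 24, t0 = 6, θ = 1: λ = 1/24, and the share reaching a TKI is 1/(1 + 6/24) = 0.800. Then 1 + (6 + u)/24 = 2 × 1.25, so u = 30.0 months from TKI start, or 36.0 from enrolment.
- Over m = 18, 24, 30; t0 = 3, 6, 9; θ = 0, 0.5, 1: 67–93% reach a TKI. Apparent median OS rises by 0–9 months with a TKI-start origin, or 3–18 months with an enrolment origin. With the TKI-start origin the shift is zero when the hazard is constant and the same for all patients (θ = 0).

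The model contains only the loss of early deaths. It leaves out forces that may act the other way.

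**5. ORR.** Assume a TKI response of about 65% and that 60–90% of the 22 reach a TKI. At 90%, 13/20 = 65% of those treated respond, but 13/22 = 59% of all. At 60%, 8/13 = 62% of those treated respond, but 8/22 = 36% of all. Over the range, the rate among those treated is 62–67% and over all 22 it is 36–59%.

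**6. Does all-patient OS fill the gap?** It counts deaths before a TKI, which is what is needed. But its time origin does not exist in this trial, it pools patients for whom a later TKI is not the planned question, and no TKI-first comparison of it is specified.

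**The case against.** The strongest reply is that objective 3 asks a narrower question: whether a TKI still works after pembrolizumab. Section 4.2.1 motivates this with melanoma data on targeted drugs after immunotherapy, and only treated patients can answer it. Neither Section 3.2 nor Section 9.1 claims that this analysis evaluates the whole sequence. This stands, and the post-TKI figures should stay as a description of TKI activity.

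The second reply is that all-patient OS is already a secondary endpoint. This also stands in part: the missing piece is a subset, a time origin, a label and a stated use, not a new endpoint.

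Third, the bias may not favour the trial. Losing early deaths tends to flatter post-TKI results. Losing patients who are still benefiting on pembrolizumab may do the opposite, and patients who have progressed may have a poorer prognosis than untreated controls. This stands, so no direction should be claimed. It does not rescue the comparison, because a bias that cannot be signed cannot support a claim of similarity.

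Fourth, the stakes are limited: this is a secondary comparison without a margin or decision rule, and the primary ORR test is unaffected. That is correct.

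**Conclusion.** The point holds in this form: the Section 9.1 comparison is conditional on surviving to and starting a TKI. It can describe TKI activity after pembrolizumab but cannot evaluate the pembrolizumab-first sequence. That the set contains only TKI starters is inferred from the wording, since the plan defines no set. The sizes rest on assumed deaths, survival, TKI start times and response rates, none of which the documents give.

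A reader might infer more than this, and the documents do not support it:

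- **That the comparison favours pembrolizumab first.** The net direction is undetermined.
- **That the plan has no outcome covering everyone.** OS is planned for front-line pembrolizumab. It is mis-timed, mixed by mutation type and not compared.
- **That the protocol itself says crossover hides OS differences here.** Section 4.1 offers only a presumption about chemotherapy arms in other trials: "presumably based on patients in the chemotherapy arms crossing over to EGFR TKIs on progression". The problem with Section 4.2.3.1 follows more simply: OS includes the effect of any later TKI.
- **That time from first dose to TKI failure should be set against TKI-first PFS.** That interval spans two lines of treatment against one, which would favour the sequence by construction.

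**What to change.** In Section 9.1:

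- **(a)** For all dosed patients with a sensitizing mutation, analyse OS from first pembrolizumab dose. Label it OS of the sequence, and use it for any comparison with TKI-first OS.
- **(b)** Report how many of these patients never start a TKI, and why: death, decline, still on pembrolizumab, other.
- **(c)** Time post-TKI PFS and OS from TKI start. Report post-TKI ORR, PFS and OS as descriptive and conditional on starting a TKI, not as evidence on the sequence.

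In Section 4.2.3.1:

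- **(d)** Replace the statement that OS shows whether pembrolizumab is comparable to TKI therapy with one saying that OS reflects pembrolizumab followed by any later TKI.

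Time from first dose to TKI progression or death may be reported descriptively, but must not be compared with single-line TKI-first PFS.

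The cost is mainly wording. Sections 5.6, 7.1.5.4 and 7.1.5.4.1 already plan follow-up for survival, TKI start and progression. A reason other than death or continuing pembrolizumab may need one extra entry on the follow-up form. TKI progression dates may be sparse, because Section 7.1.5.4.1 expects visit frequency to vary, but the planned post-TKI PFS has that limit already and (a) does not depend on those dates. The sequence result may look less favourable than the post-TKI figures. The change removes the conditioning only: the external control remains unnamed and unadjusted.
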